11.5. CV Outcomes and Efficacy Analyses

11.5.1. CV Outcomes (Primary Efficacy Endpoint)

The primary endpoint for CV benefit will be time to MACE, which is calculated as the time from randomization to the first occurrence of MACE. The statistical hypothesis will be:

$H_{0(1.0)}$: the HR = 1.0, versus $H_{1(1.0)}$: the HR \neq 1.0.

The primary analysis will be based on the ITT analysis set and the MACE events determined by the EAC to meet prespecified criteria. The primary comparison of canagliflozin to placebo will be based on the HR estimate derived from Cox proportional hazards model with terms for treatment, history of a previous CV event as fixed effects.

The assumption of the proportional HR will be examined. In case the assumption is deemed not reasonable, sensitivity analyses that do not rely on the constant HR assumption will be conducted to verify the results of the primary analysis.

Additionally, the HR and its 2-sided 95% CIs versus placebo will be assessed for each dose of canagliflozin. For individual components of the composite CV endpoint, the HR

and its 2-sided 95% CIs of canagliflozin combined doses relative to placebo will also be assessed.

Sensitivity analyses including CV endpoint events that occur within 30 days of the last dose of blinded study medication will be done.

The effects of different baseline demographic variables (eg, age, race, sex) as well as other important baseline disease characteristics (eg, history of prior CV disease, key concomitant therapy use, and region) on the primary endpoint will be explored; a detailed discussion of subgroup analyses will be provided in a SAP for this study, which will be finalized before the first interim analysis.

11.5.2. Major Secondary Efficacy Endpoints

The continuous secondary efficacy endpoint, change from baseline in HOMA-B will be analyzed using an analysis of covariance (ANCOVA) model with treatment (canagliflozin 100 mg, canagliflozin 300 mg or placebo) and stratification factors as fixed effects and the corresponding baseline value as a covariate. The treatment difference (each dose of canagliflozin minus placebo) in the least-squares means and the 2-sided 95% CI will be estimated based on this model. The analyses for beta-cell function will be conducted on subjects not receiving insulin at randomization and, for subjects who are started on insulin during the study, the last data point before the initiation of insulin will be included for these analyses.

The categorical secondary efficacy endpoint is the proportion of subjects with progression of albuminuria (defined as ≥ 1 step increase, ie, no albuminuria to micro- or macro-albuminuria or from micro-albuminuria to macro-albuminuria). The proportion of subjects with progression of albuminuria will be analyzed using the logistic model with treatment (canagliflozin 100 mg, canagliflozin 300 mg or placebo), and stratification factors as a fixed effect. Albuminuria will be assessed according to the categorizations defined in the National Kidney Foundation Kidney Disease Outcomes Quality Initiative Guideline #1 (KDOQI 2007): the definition of micro-albuminuria is albumin/creatinine ratio of 30 to 300 mg/g, and the definition of macro-albuminuria is albumin/creatinine ratio greater than 300 mg/g.

For the secondary endpoints of HOMA-B and proportion of subjects with progression of albuminuria, the analyses will compare the dose groups, *combined* and *individually*, relative to placebo.

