The effects of different baseline demographic variables (eg, age, race, sex) as well as other important baseline disease characteristics (eg, history of prior CV disease, key concomitant therapy use, and region) on the primary endpoint will be explored; a detailed discussion of subgroup analyses will be provided in a SAP for this study which will be finalized before the first interim analysis.

Major Secondary Efficacy Analysis

Changes from baseline in the continuous variables of HOMA-B and the proinsulin/insulin ratio, HbA_{1c}, FPG, blood pressure, body weight, albuminuria, and eGFR, and percent change in fasting lipids will be analyzed using an analysis of covariance (ANCOVA) model with treatment (canagliflozin 100 mg, canagliflozin 300 mg, or placebo), and stratification factors as a fixed effect and the corresponding baseline value as a covariate. The treatment difference (each dose of canagliflozin minus placebo) in the least-squares means and the 2-sided 95% CI will be estimated based on this model. The analyses for beta-cell function will be conducted on subjects not receiving insulin at randomization and, for subjects who are started on insulin during the study, the last data point before the initiation of insulin will be included for these analyses.

The categorical secondary efficacy endpoint is the proportion of subjects with progression of albuminuria (defined as ≥ 1 step increase, ie, no albuminuria to micro- or macro-albuminuria or from micro-albuminuria to macro-albuminuria). The proportion of subjects with progression of albuminuria will be analyzed using

the logistic model with treatment (canagliflozin 100 mg, canagliflozin 300 mg or placebo) and stratification factors as a fixed effect.

Multiplicity Adjustment

To ensure the family-wise Type I error rate (alpha level) in this study is at most 5%, a gatekeeping procedure will be applied in testing the primary and secondary hypotheses.

Interim Analysis

Interim analyses of CANVAS will be done to prepare: (1) an interim safety report in support of the initial health authority filing, (2) the 18-week substudy reports, and (3) the CV safety meta-analyses (based on adjudicated data). The interim data from the CANVAS study will primarily supplement the safety and tolerability data generated from other studies in the canagliflozin development program.

TIME AND EVENTS SCHEDULE (CONTINUED)

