- ^g Record as prestudy therapy any medications taken from 30 days before screening (except for AHAs; record AHAs taken within 12 months of screening).
- ^h Subjects will receive information regarding the symptoms of and treatment for hypoglycemia. Signs and symptoms of hypoglycemia (and concurrent fingerstick glucose measurement, if available) should be captured in the subject diary, which should be brought to the study center for review by research study staff.
- ⁱ Full physical examination will include a full review of body systems (vital signs, as below, head and neck, eyes, chest and lungs, breast, CV, extremities and back, abdomen, and neurological examination). A pelvic/genitourinary system examination (ie, prostate, rectal, and gynecologic examinations) should be performed if considered clinically appropriate by the investigator.
- ^j Vital signs (to be taken before blood collection for laboratory tests) will consist of 1 pulse and 3 blood pressure measurements (sitting position, after sitting for 5 minutes; record 3 consecutive blood pressure readings, at intervals of at least 1 minute apart). Consistent with standard diabetes treatment guidelines, all study participants should be provided with routine preventative foot care and early intervention for foot problems (see Section 12.2.1 All Adverse Events for further detail).
- ^k Only required before a 52-week interval visit, regardless of whether the subject is coming for in-clinic visits every 13 or 26 weeks.
- ^l Medical resource utilization (MRU) data should be collected in the subject diary. A sample list of MRU questions contained in the diary is provided in Attachment 9.
- ^m Specific details about specimen collection, storage, packaging, and shipping will be provided in operations manuals. For fasting plasma glucose, insulin, proinsulin, C-peptide, and lipids, subjects must be fasting for at least 8 hours before blood sample collection, except for the screening visit when nonfasting blood samples may be collected. The first morning void specimens will be used to measure albumin and creatinine. A set of plasma, serum, and urine samples for exploratory analysis will be collected at each specified time point. (Specific details about specimen collection, storage, packaging, and shipping are provided in Attachment 4.) The urine collections for routine urinalyses and exploratory specimens should be obtained from a spot urine specimen in the clinic.

(Continued)

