5. TREATMENT ALLOCATION

To ensure sufficient experience in subjects with documented, pre-existing CV disease—the highest risk group—approximately 70% (minimum of 60%) of subjects (globally) are targeted to be in this group.

Stratification for Substudies

Subjects will have within-subgroup balanced (1:1:1) randomization to each of the 3 treatment groups within the following 6 predefined strata, which are based upon AHA medication(s) that the subject is receiving at the run-in visit and will be continuing at entry into the double-blind treatment phase:

- Stratum 1: insulin monotherapy ≥ 20 units per day, on stable doses at least 10 weeks before the run-in visit
- Stratum 2: insulin ≥ 20 units per day plus metformin, on stable doses at least 10 weeks before the run-in visit, and no other background AHA therapy
- Stratum 3: insulin ≥ 20 units per day plus any other AHA(s) on stable dose(s) for at least 10 weeks before the run-in visit
- Stratum 4: sulfonylurea monotherapy (at doses specified in [Attachment 1](#)), on stable doses at least 10 weeks before the run-in visit
- Stratum 5: pioglitazone ≥ 30 mg/day plus metformin $\geq 2,000$ mg/day (or at least 1,500 mg/day for subjects who have a history of not being able to tolerate higher metformin doses) and no other background AHA therapy, on stable doses at least 10 weeks before the run-in visit
- Stratum 6: subjects not in one of the above AHA subgroups

Note: a stable dose of insulin is defined as no change in the insulin regimen (ie, type[s] of insulin) and $\leq 15\%$ change in the average total daily dose of insulin (as averaged over one week).

The stratification process will be handled via queries in the Interactive Voice Response System (IVRS) or after logging on to the Interactive Web Response System (IWRS) being used for the study, described below.

Randomization and Blinding Procedures

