Central randomization will be implemented in this study. Subjects will be randomly assigned to 1 of 3 treatment groups based on a computer-generated randomization schedule prepared by or under the supervision of the sponsor before the study. The randomization will be balanced by using randomly permuted blocks and will be stratified based on the use of specific concomitant antihyperglycemic medications at baseline (as noted above). Based on this randomization schedule, the study drug will be packaged and labeled. Medication numbers will be preprinted on the study drug labels and assigned as subjects qualify for the study and are assigned to double-blind treatment.

At baseline (Day 1), the randomization number and medication numbers, the treatment code, which is linked to the randomization schedule, will be assigned after telephoning into the IVRS or after logging on to the IWRS designated by the sponsor. The requestor must use his/her own user identification (ID) and personal identification number (PIN) when contacting the IVRS/IWRS, and will then give the relevant subject details to uniquely identify the subject. Based on this information, the IVRS/IWRS will assign a unique treatment code, which will dictate the treatment assignment and study drug kit for the subject. As subjects are randomly assigned to treatment, the IVRS/IWRS will assign a study drug kit to be dispensed at that visit. New medication numbers will be assigned each time the IVRS/IWRS is contacted for dispensing additional study drug. The randomization (or initial subject allocation) number at baseline will be the identifying number linking all subsequent kits to the individual subject.

The study drugs will be identical in appearance and will be packaged in identical containers.

The randomization code that links the randomization number assigned to the subject with a treatment group assignment will be maintained within the IVRS/IWRS. This randomization code will not be provided to the investigator unless required, as described below, for unblinding in emergency situations.

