11.5.4. Additional Secondary Efficacy Endpoints

Additional efficacy endpoints of interest will include the following:

- changes from baseline to end-of-treatment in the proinsulin/insulin ratio (in a subset of subjects), urinary albumin/creatinine ratio, and eGFR
- changes from baseline to Week 18 in HbA_{1c}, FPG, systolic and diastolic blood pressure, and body weight
- percent change from baseline to Week 18 in fasting plasma lipids (triglycerides, HDL-C, LDL-C, total cholesterol, and the ratio of LDL-C to HDL-C)

The continuous secondary efficacy endpoints, changes from baseline in the proinsulin/insulin ratio, HbA_{1c}, FPG, body weight, blood pressure, albuminuria, and eGFR and percent change in fasting lipids will be analyzed in the same manner as the secondary efficacy endpoint, change from baseline in HOMA-B.

For the assessment of change from baseline in HbA_{1c} at Week 18, subgroup analyses (described in detail in the SAP for this study) will be conducted to enhance understanding of factors that might impact glycemic response to canagliflozin.

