11.9.3. Efficacy Analyses

For each substudy, except the sulfonylurea substudy as noted above, the primary efficacy analysis will only be performed when sufficient subjects (≥ 258) in the subpopulation are

randomized in each of the 3 treatment groups (≥ 86 per group). The analysis will be conducted when the sponsor prepares for the regulatory submissions. For the sulfonylurea substudy, the primary efficacy analysis will only be performed when sufficient subjects (≥ 150) in the subpopulation are randomized in each of the 3 treatment groups (≥ 50 per group).

[figure not shown]
The primary efficacy endpoint will be the change in HbA_{1c} from baseline through Week 18. The LOCF method will be applied when the Week 18 values are missing. In subjects receiving rescue therapy, their measurements made before rescue will be used as the last observation. An ANCOVA model with treatment as a fixed effect and the corresponding baseline value as covariate will be used. The treatment difference (each dose of canagliflozin minus placebo) in the least-squares means and the 2-sided 95% CI will be estimated based on this model.

As a supportive analysis, change from baseline in HbA_{1c} will be analyzed using a restricted maximum likelihood (REML) based on repeated measures approach. The analysis will be based on observed data and will include the fixed, categorical effects of treatment, visit, and treatment-by-visit interaction, as well as the continuous, fixed covariates of baseline and baseline-by-visit interaction. An unstructured covariance will be used to model the within-subject errors. The treatment comparisons will be made between each dose of canagliflozin and placebo at Week 18 and significance tests will be based on the difference of the least-squares means.

The secondary efficacy evaluations of change in body weight, FPG, and systolic and diastolic blood pressure, and percent change in fasting plasma lipids will be analyzed using an ANCOVA model similar to that used in the primary efficacy analysis. The percentage of subjects with HbA_{1c} $< 7\%$ at Week 18 will be assessed by means of a logistic model with treatment and stratification factors as fixed effects and baseline HbA_{1c} as a covariate.

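### The alpha-controlled model for albuminuria progression leaves out baseline albuminuria; adding baseline category and log ratio together would gain about 4 to 9 power points per dose under plausible assumptions.

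*Protocol*

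**What the plan says.** Section 11.5.2 lists the terms of the albuminuria-progression model: "The proportion of subjects with progression of albuminuria will be analyzed using the logistic model with treatment" (three levels) and stratification factors. The synopsis repeats this: "the logistic model with treatment (canagliflozin 100 mg, canagliflozin 300 mg or placebo) and stratification factors as a fixed effect". No baseline albuminuria term appears in either place.

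The stratification factors are the six groups in section 5, "which are based upon AHA medication(s) that the subject is receiving at the run-in visit". The same section says that the randomisation "will be stratified based on the use of specific concomitant antihyperglycemic medications at baseline". Albuminuria is not among them.

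Elsewhere the protocol does name a baseline term:
- HOMA-B, in the same section 11.5.2: "stratification factors as fixed effects and the corresponding baseline value as a covariate".
- The additional continuous endpoints, including albuminuria as a continuous measure, in section 11.5.4: "will be analyzed in the same manner as the secondary efficacy endpoint, change from baseline in HOMA-B".
- The other logistic model, for HbA1c below 7% in the substudies (section 11.9.3): "logistic model with treatment and stratification factors as fixed effects and baseline" HbA1c.

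Under section 11.5.3 albuminuria progression is tested for each dose against placebo, after MACE, within a 5% family-wise error rate.

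**The concern.** Progression is a step up in category, so it means crossing 30 or 300 mg/g. A subject's risk therefore depends on the starting category and on the distance to the next threshold. Subjects enter in all three categories, and those already macro-albuminuric cannot progress. A strongly prognostic variable, without which the endpoint cannot be scored, is thus missing from the model.

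Section 11 leaves specific details to the SAP, but here the protocol names the terms and omits baseline, while its comparable models include it. Power is at stake on a formal secondary hypothesis; validity is not.

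**Working it through.** **1. The protocol's own power figures.** The only main-study power statement is for MACE (section 11.3): about 400 events, two-sided 0.05, giving 33%, 55% and 76% for HR 0.85, 0.80 and 0.75. With 2:1 allocation (combined doses versus placebo), power = Φ(|ln HR| × √(400 × 1/3 × 2/3) − 1.96):
- HR 0.85: Φ(1.532 − 1.96) = 33.4%
- HR 0.80: Φ(2.104 − 1.96) = 55.7%
- HR 0.75: Φ(2.712 − 1.96) = 77.4%

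These agree with the stated values to within 2 points. They are used below because MACE is the gate.

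**2. Inputs for albuminuria.** From the protocol: 4,330 subjects randomised 1:1:1 (4,330/3 ≈ 1,443 per arm), cut-points 30 and 300 mg/g, and 5% annual dropout. Everything else is assumed. The base case takes a log-normal baseline ratio with median 14 mg/g and log-SD 1.5, measurement SD 0.4, and a log slope with mean 0.04 and SD 0.15 per year. Follow-up is at most 6.5 years, the last value is used, and an effect e shifts the log ratio by log(1 − e). There were 3,000 simulated trials per scenario.

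**3. Shape of the baseline risk.** Simulated placebo progression by baseline ratio:

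| Baseline (mg/g) | Progression |
|---|---|
| 20–30 | 49% |
| 30–60 | 5% |
| 200–300 | 42% |
| above 300 | 0% |

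The profile is a sawtooth. A straight line in log ratio cannot follow it and neither can three category means; together they follow it much better.

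**4. Check of the simulation.** Base-case progression is 16.4% on placebo and 14.5%, 13.5% and 12.6% for a 10%, 15% and 20% reduction in the ratio. The closed form is Φ(d/√{[p₀(1−p₀)+p₁(1−p₁)]/1,443} − 1.96), with d = p₀ − p₁. It gives 29.2%, 59.0% and 82.7%, against 29.1%, 58.1% and 82.9% simulated for the model as written.

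**5. Power per dose, two-sided 0.05 (%).**

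| Scenario | As written | Log ratio only | Category only | Both |
|---|---|---|---|---|
| Base, 10% effect | 29.1 | 29.9 | 29.5 | 34.2 |
| Base, 15% | 58.1 | 58.8 | 58.3 | 65.6 |
| Base, 20% | 82.9 | 83.5 | 82.9 | 89.2 |
| Median 18, SD 1.8, 15% | 57.3 | 58.0 | 58.2 | 66.0 |
| Measurement SD 0.8, 20% | 72.0 | 72.2 | 72.7 | 77.2 |
| Slope SD 0.25, 15% | 40.0 | 40.4 | 40.3 | 43.7 |

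Over 12 effect scenarios the two-term gain is 3.8 to 8.7 points (paired SE 0.4 to 0.5). Log ratio alone gains 0.2 to 1.1, or 1.0 to 2.7 if fitted only to subjects who can progress. Category alone gains 0.1 to 0.9. The squared ratio of mean z-statistics, two-term against as written, is 1.12 to 1.22, hence 12 to 22% more subjects. Null rejection is 4.8% as written and 4.7% with both terms.

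**6. Different assumptions.** A separate simulation used a simple baseline-to-end change model and 48 scenarios. The two terms together gained 3.0 to 10.0 points, mostly 5 to 9; either alone gained −0.7 to +2.5. With a skewed baseline (70/22/8% normal/micro/macro) the two-term gain depended on the SD of the log change: 6.4 to 7.7 points at SD 0.8, 3.1 to 4.1 at 1.1, and 1.5 to 2.9 at 1.4. Null rejection was 5 to 6% for every model.

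**7. Other alpha levels and the gate.** Alpha allocation is left to the SAP. The two-term gain is 3.5 to 8.7 points at 0.025 and 2.3 to 10.5 at 0.0125. For the doses combined at 0.05 it is 3.0 to 7.8. If the albuminuria result is independent of the MACE gate, the unconditional gain runs from 3.8 × 0.33 = 1.3 to 8.7 × 0.76 = 6.6 points.

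**The case against.** The best reply is that nothing here is wrong. The randomised comparison keeps its error rate, the endpoint is already defined relative to each subject's own baseline category, and the SAP may add covariates. Consistency with the protocol's other models would justify only a single linear baseline term, which buys about 0 to 3 points; the larger gain needs a two-term model that the protocol uses nowhere. The size rests wholly on outside assumptions and drops to 1.5 to 3 points in the least favourable case. The formal test is reached only if MACE succeeds.

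There is also a credibility cost. Section 11.8.1 has efficacy as well as CV results exported for submissions, with sponsor personnel unblinded, so a late change to an alpha-controlled model can be challenged as post hoc. The category term also has a macro-albuminuria coefficient that cannot be estimated.

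Most of this stands as a limit on importance: the issue is efficiency, its size is conditional, and the credibility cost is real. It does not remove the point. The gain was positive in every scenario run with an effect, the covariates are measured before randomisation, and the protocol itself fixed the deficient term list.

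**Conclusion.** The concern holds. The model for a gatekept secondary endpoint omits its strongest predictor. Including baseline category and log ratio together would raise power per dose by roughly 4 to 9 points with a log-normal baseline, and by as little as 1.5 to 3 with a skewed baseline and very noisy change. These figures assume that the drug lowers the ratio itself, and they depend on ratio distributions and effect sizes that the protocol does not give. Type I error is unaffected either way, and the trial is not threatened. The change should be made, but it is not essential.

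**What to change.** In section 11.5.2 and the synopsis, specify logistic regression of progression on treatment and stratification factors as fixed effects, with two added covariates: baseline albuminuria category and log-transformed baseline albumin/creatinine ratio. Name both, since either alone achieves little. Report adjusted proportions or a standardised risk difference beside the odds ratio.

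The change is wording and programming only; endpoint, population and comparisons stay as they are. No new data are needed, as the Time and Events Schedule footnotes confirm: "The first morning void specimens will be used to measure albumin and creatinine". Three costs should be dealt with in the text:
- **Effect measure.** The adjusted odds ratio is conditional and lies further from 1 (base case, 15% effect: 0.80 as written, 0.76 adjusted), hence the adjusted proportions.
- **Macro-albuminuria at baseline.** That category has no events, so its coefficient cannot be estimated. State that this is expected and that these subjects stay in the analysis. In one simulated trial the treatment estimates (−0.345 and −0.214; SE 0.118 and 0.119) were identical with and without them.
- **Timing.** This is the main cost. Because sponsor personnel have seen interim data (sections 1.2 and 11.8.1), date the change before final unblinding, record who made it and what results they had seen, and state that it rests only on pre-randomisation variables.
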